#### 1. PROJECT TITLE

Effect of Peripheral Oxytocin on Touch Pleasantness and Pain

#### 4. ESTIMATED DURATION OF THE STUDY

The proposed project will be ongoing for up to two years.

#### 5. LAY LANGUAGE SUMMARY OR SYNOPSIS (no more than one paragraph)

Research shows that slow gentle skin stroking can activate special sensory nerves in the skin that elicit relaxing effects on the body and mind, similar to the effects of the hormone oxytocin. Studies also suggest that gentle stroking may even release oxytocin in the skin. However, we do not know what oxytocin does in the skin and how it affects nerves that send pleasant touch or pain signals to the brain. The proposed study will determine how individuals perceive gentle stroking and experimental pain before and after a skin injection of oxytocin compared to a placebo injection. This research will determine the role of oxytocin in affective touch and pain perception and whether it may have clinical potential to relieve pain.

#### 6. SPECIFIC AIMS

#### Aim 1: Assess whether subcutaneous injection of oxytocin versus saline placebo has local antinociceptive effects on experimental pain.

**Hypotheses:** We hypothesize that OT will reduce pain threshold and ratings of pain intensity and unpleasantness for thermal, mechanical, and pressure pain.

# Aim 2. Assess whether subcutaneous injection of OT versus saline placebo alters local pleasantness of CT gentle stroking.

**Hypotheses:** We hypothesize that OT will increase touch pleasantness of slow versus fast stroking and will increase heart rate variability.

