Effects of OT on pleasant touch have been tested through the intranasal route of administration. Chen and colleagues tested the effect of 24IU intranasal OT on 40 male subjects in a cross-over design administering positive, neutral, and negative valence touch on the arm with velocities targeting C-tactile afferents. OT significantly increased touch pleasantness ratings independent of touch valence (estimated Cohens d = 3), with the effect largely driven by negative stimuli. This study provided the first evidence that OT may enhance rewarding effects of touch, regardless of valence. In addition, the same group administered manual or machine foot massage to 46 male participants. Intranasal OT significantly increased pleasantness ratings for manual massage, supporting the importance of OT for enhancing positive responses to social touch.

The proposed ACTRI pilot research project will identify the effect of subcutaneous oxytocin on experimental pain and pleasant CT stroking. This contribution will be significant as it will provide foundational knowledge about the role of peripheral OT in perception of affective touch and pain. This is important because pathological states alter affective touch perception and may involve corresponding changes in the role of peripheral OT in affective touch pathways, with potential significance for therapeutic use of peripheral OT. The central hypothesis is that OT will reduce pain threshold and ratings of pain intensity and unpleasantness for thermal, mechanical, and pressure pain. Further, we predict that OT will increase touch pleasantness of slow versus fast stroking and will increase heart rate variability. This research will advance our understanding of the mechanisms of touch-based therapies, such as massage, and identify potential targets for noninvasive modulation of affect and pain.

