# Affective touch perception:

Affective touch testing will be comprised of 2 trials of 15s slow brushing and 2 trials of 15s fast brushing on each dorsal forearm, in a random order. After each trial participants will rate the (un)pleasantness and intensity of the sensation on VAS scales.

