#### Outcome Measure(s)

#### Primary Outcomes:

- Pleasantness ratings of slow (primary) and fast gentle brushing
- Pain perception assessed in response to noxious pinprick (primary), pressure, and heat stimulation.
- Pain intensity and (un)pleasantness will be assessed with visual analog scales (VAS) as follows: pain intensity [anchors "no pain" (far left) to "most intense pain imaginable" (far right)] and (un)pleasantness ["extremely unpleasant" (far left) to "neutral" (middle) to "extremely pleasant" (far right)]. 100-point VAS scales are common, validated, and reliable measures of pain.

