# Sample Size Determination & Power

We expect that pleasantness ratings of C-LTMR-optimal touch will be significantly increased after local OT injection and that pain perception will be reduced. In published studies, differences in postsurgical pain after local infiltration with OT versus control resulted in very large mean differences in VAS pain ratings of Cohen's d = 3 to 4.5. In spinal nerve ligation (SNL) model rats, interplantar injection of OT versus control resulted in mean differences in paw withdrawal threshold of Cohen's  $d = 13.8^{19}$ . In addition, intranasal oxytocin (24IU) increases pleasantness of touch stimuli (especially driven by negative stimuli), with an estimated Cohen's d of  $\sim 3^{23}$ . Although these are very large effect sizes, accounting for sampling variability and differences in proposed study design (acute pain; healthy adults; subcutaneous OT administration), we powered the study to detect a large effect size of d = 0.8. Assuming a within-subject correlation of 0.5 and an attrition rate of 25%,

the proposed sample size of N = 20 will provide 0.8 power to detect an effect size as small as d = 0.8 based on a two-sided  $\alpha = 0.05$ .

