## **Data Analyses and Interpretation**

General Statistical Approaches. Data will be analyzed descriptively and analytically. Descriptive statistics (means and standard deviations for continuous and proportions/counts for categorical outcomes) will be used to describe outcomes at baseline. Weighted generalized estimating equations (WGEE) will be employed, with appropriate link functions depending on the type of the response (e.g., identity for continuous and logit for binary outcome), to examine longitudinal changes in an outcome and longitudinal association between outcomes in regression analysis, controlling for covariates for Aims 1-2. Unlike parametric models such as generalized linear mixed-effects models (GLMM), the semi-parametric WGEE requires no distribution assumption and yields valid inference for a broader class of data distribution under the missing at random mechanism^123. WGEE provides valid inferences under the missing at random (MAR) mechanism^124. We will use WGEE to test the missing completely at random (MCAR) assumption and will use the generalized estimating equations (GEE), if the MCAR is not rejected. GEE involves fewer parameters and provides more efficient inference than WGEE. Given the small sample size for Aims 1-2, we will complement the usual asymptotic inference with clustered bootstrap to improve inference validity and report the bootstrap inference if it differs from its asymptotic counterpart. We set  $\alpha$ =0.05 for all analyses and use Holm-Bonferroni adjustments for <= 5 tests and False Discovery Rate (FDR) for > 5 tests. When correlated outcomes are analyzed (e.g., outcomes in related domains), corrections will be calculated based on the effective number of independent tests that account for correlations between the outcomes. Whenever possible, effect size will be reported in addition to point and interval estimates. All analyses will be performed using the latest versions of R^129 and SAS. Hypothesis Testing. For Aim 1, separately for OT and saline placebo sessions, we will compare changes in ratings of pain over time between the OT and control arm using WGEE, where time (one binary indicator) will be the predictor, controlling for covariates. A significant time effect, tested using appropriate linear contrasts, will support the hypothesis that the OT injection has effects on the outcome. We will follow with *post hoc* analyses to estimate the effect size of the OT injection. For Aim 2, we will apply the same approach in Aim 1 to pleasant touch outcome. Age and race/ethnicity will be included as potential covariates in all analyses.

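### Aim 2 predicts an oxytocin effect on slow versus fast stroking, but the analysis has no speed term and specifies no slow-fast contrast

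*Combined protocol and SAP*

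**What the plan says.** The speed comparison is in the Aim 2 hypothesis, "We hypothesize that OT will increase touch pleasantness of slow versus fast stroking and will increase heart rate variability", and again at the end of section 7 (Background and Significance): "we predict that OT will increase touch pleasantness of slow versus fast stroking and will increase heart rate variability". The title of Aim 2 is broader. It asks only whether oxytocin, compared with saline, alters the pleasantness of CT stroking.

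The data for a comparison of speeds are collected. Under Affective touch perception, each testing block has "2 trials of 15s slow brushing and 2 trials of 15s fast brushing on each dorsal forearm", in random order, and the touch testing is repeated after injection. Primary Outcomes lists "Pleasantness ratings of slow (primary) and fast gentle brushing" and defines no difference between the two. Sample Size Determination & Power speaks only of the slow stimulus: "We expect that pleasantness ratings of C-LTMR-optimal touch will be significantly increased after local OT injection".

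The analysis is in Data Analyses and Interpretation. The Aim 1 comparison is described as follows: "separately for OT and saline placebo sessions, we will compare changes in ratings of pain over time between the OT and control arm". The method is weighted GEE, and the model is given as one "where time (one binary indicator) will be the predictor, controlling for covariates". Support for the hypothesis is to come from a significant time effect tested by linear contrasts that are not spelled out. The Hypothesis Testing text names age and race/ethnicity as potential covariates. Aim 2 has one sentence: "For Aim 2, we will apply the same approach in Aim 1 to pleasant touch outcome".

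**The concern.** The hypothesis is a treatment-by-speed statement: the oxytocin effect should be larger for slow than for fast stroking. The analysis treats pleasant touch as a single outcome and asks whether it changes over time, session by session. Nothing in it estimates how the effect differs between speeds.

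This matters because fast brushing is the natural comparator for the CT rationale in section 7. If oxytocin simply made all touch more pleasant, the primary slow rating would rise as well. A null slow result would count against the predicted increase, but a positive one would leave the slow-versus-fast question open. With no contrast fixed in advance, any statement about CT specificity would rest on a comparison chosen after the data were seen.

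**Working it through.** **1. The plan's own sample size.** Inputs from Sample Size Determination & Power: d = 0.8, within-subject correlation 0.5, two-sided alpha 0.05, power 0.8, attrition 25%, N = 20.

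For a paired t-test, dz = d / sqrt(2(1 − 0.5)) = 0.8 / 1 = 0.8. Non-central t power is 0.790 with 14 pairs and 0.821 with 15. So 15 completers are needed, and 15 / 0.75 = 20. The stated N reproduces. It covers one within-subject difference, not a difference between two such differences.

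**2. What a slow-only test can show.** Take a direct oxytocin-versus-saline paired comparison of slow pleasantness on the injected forearm, with 15 completers and dz = 0.8.

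- Oxytocin acts on slow only: power 0.821.
- Oxytocin acts equally on slow and fast: power 0.821.

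The test is the same in both cases because fast ratings do not enter it. Under equal effects, a slow-minus-fast contrast would reject only at its error rate of 0.05.

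**3. What a slow-fast contrast could show.** Two inputs are assumed because the documents give neither: rho, the correlation between the slow and fast treatment differences, and f, the fast effect as a fraction of the slow effect. With equal variances,

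dz(contrast) = d(1 − f) / sqrt(2 − 2·rho).

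Example: d = 0.8, f = 0, rho = 0 gives 0.8 / sqrt(2) = 0.566.

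Power with 15 completers (14 df), two-sided 0.05:

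| d | f | rho = 0 | rho = 0.25 | rho = 0.5 | rho = 0.75 |
|---|---|---|---|---|---|
| 0.8 | 0 | 0.53 | 0.65 | 0.82 | 0.98 |
| 0.8 | 0.5 | 0.18 | 0.22 | 0.30 | 0.53 |
| 0.5 | 0 | 0.25 | 0.31 | 0.44 | 0.72 |
| 0.5 | 0.5 | 0.10 | 0.11 | 0.15 | 0.25 |

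**4. Effect of using change scores.** The table is for a single paired difference. If the contrast is a pre-to-post change, let c be the pre-post correlation of each participant's oxytocin-minus-saline, slow-minus-fast difference. With equal variances before and after, dz is further divided by sqrt(2 − 2c). The divisor is 1 at c = 0.5, so the table then stands. Power is lower if c is below 0.5 and higher if it is above. The documents give no value for c.

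**The case against.** The strongest reply is that most of Aim 2 is covered. Its title makes no comparison with fast stroking, slow brushing is labelled primary, the power section expects a rise in slow touch, and this is a pilot. That stands, and it limits the point. A reader might infer that Aim 2 goes untested or that the touch outcome is undeclared. The documents do not support that: the gap is the slow-versus-fast clause, which appears twice.

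A second reply is that the unspecified linear contrasts could include a speed contrast. The wording does not rule it out. But those contrasts are attached to the time effect in a model with no speed term, so the most that can be said is that a slow-fast contrast was left open, not planned.

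A third tempting inference is that the investigators will read a significant slow test beside a non-significant fast test as specificity. Under equal effects that pattern would appear in about 8% to 15% of trials at d = 0.8 and 12% to 25% at d = 0.5 (simulation, rho from 0.75 down to 0). No passage says the results would be read that way, so this shows why a contrast helps and is not a predicted error rate.

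Finally, the figures assume a direct between-session comparison. The plan fits the sessions separately, so 82% is not the power of the slow analysis as written. That is correct, and the figures are illustrative. The logical point does not depend on them.

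Heart rate variability sits in the same hypothesis sentence, but it is a separate matter and adds no weight here.

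**Conclusion.** The point holds as an omission that should be corrected. As written, the Aim 2 analysis cannot support the slow-versus-fast hypothesis, because it has no speed term and no slow-fast contrast is specified. The slow-brushing primary outcome is unaffected and still answers the Aim 2 title.

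The size is best seen in the slow test's inability to discriminate: 82% significant under a slow-only effect and 82% under an equal effect. This assumes 15 completers, d = 0.8, within-subject correlation 0.5 and a direct oxytocin-versus-saline comparison. Whether N = 20 is enough for the contrast cannot be settled from the documents. Across the assumed rho and f, power runs from 0.10 to 0.98.

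**What to change.** 1. Keep slow-brushing pleasantness as the primary touch outcome.
2. Pre-specify one treatment-by-speed contrast: the oxytocin-versus-saline difference in the pre-to-post change of slow-minus-fast pleasantness on the injected forearm. A baseline-adjusted post-injection value would also serve. Either form uses the pre-injection ratings and fits the plan's focus on change over time.
3. Require this contrast for any slow-versus-fast or CT-specific claim. Otherwise limit the conclusion to slow touch.
4. State that it is a between-session comparison added to the session-by-session models.
5. Place it as a secondary test within the existing Holm/FDR rule. Testing it in fixed order after slow is optional. A gate lets a missed slow result block the very hypothesis at issue.

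The cost is wording in the analysis section and the outcome list, with no extra participants, visits or stimuli. The downside to state openly is the uncertain power shown in the table. Change scores would shift those figures with the pre-post correlation, and any multiplicity adjustment below 0.05 would lower them. A non-significant contrast should therefore not be read as evidence that oxytocin affects both speeds equally. If the investigators meant only slow touch, the alternative is to reword the hypothesis in section 6 and section 7 to match the analysis.

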#### 7. BACKGROUND AND SIGNIFICANCE

Given the major burden of chronic pain in the U.S., there is an urgent need to understand basic mechanisms of chronic pain and develop effective interventions, including nonpharmacologic approaches like massage. While massage is widely sought for its effects of pleasant relaxation and pain reduction, the neural mechanisms underlying affective touch and its effects on pain are poorly understood. A clear understanding of basic pathways for touch-based therapies is needed to understand the mechanisms of their effects on pain and mood, determine changes in chronic pain conditions, and identify potential targets for noninvasive modulation of affect and pain.

Thickly myelinated A $\alpha$  and A $\beta$  afferent sensory fibers rapidly conduct proprioceptive and touch signals to the brain, while thinly myelinated A $\delta$  and unmyelinated C-fibers transmit temperature, chemical, and pain signals at a slower speed. A large body of evidence demonstrates that a subset of unmyelinated C-fibers known as C-tactile (CT) afferents project to the insula and convey the pleasant sensation of stroking on hairy skin, leading to theories of a privileged CT pathway for affective touch as well as pain reduction. As predicted by this model, patients with reduced C-fiber afference show reduced preference for slow stroking, while patients with myelinated A-fiber deafferentation retain its pleasantness and insula response. Furthermore, slow (CT-

optimal) versus fast touch induces affective alterations including positive mood and increased heart rate variability.

Oxytocin (OT) is a neuropeptide broadly implicated in social behavior. Systemic administration of OT reduces stress and anxiety and increases trust. In addition, OT exerts antinociceptive and analgesic effects in both humans and rodent models. Given the similar effects of CT stimulation and systemic OT, OT is a proposed mediator for the affective effects of CT touch. Indeed, stimulation of sensory afferents induces OT release, and intranasal OT increases touch pleasantness. OT directly modulates wide dynamic range neurons in the spinal cord and C-fiber excitability. These mechanisms may be engaged by social skin touch, potentially mediated by keratinocytes. Recent research in rodents demonstrates that OT also exerts powerful effects in the periphery, where OTRs on nociceptive terminal axons can inhibit nociceptive input. Indeed, injection of OT into the paw reduced pain behavior in a neuropathic pain model, selectively in the injured paw. Furthermore, in mice, OT injected in the ganglion reverses hypersensitization of HTMRs and hyperpolarization of LTMRs that is induced by nerve injury. These studies demonstrate a local modulation of pain by peripheral OT.

OT is not used clinically because it cannot penetrate the blood-brain barrier, has poor specificity and a short duration of effect, and cannot be patented. However, only one study has tested the effect of peripheral OT in humans, demonstrating reduced postsurgical pain after subcutaneous OT injection prior to gallbladder surgery. The OT group (N = 10) received subcutaneous OT (Oxitopisa, 4µg in 4ml of saline) in each of the surgical sites before surgical incisions were made. Pain was marginally reduced after surgery (Cohen's d = 3.53) and was significantly reduced upon discharge (Cohen's d = 4.16) and 24 hours after surgery (d = 4.51). These effects have not been tested in healthy adults undergoing acute pain. These findings reveal a significant gap in our understanding of the role of peripheral oxytocin in the pathways for affective touch and pain.

Effects of OT on pleasant touch have been tested through the intranasal route of administration. Chen and colleagues tested the effect of 24IU intranasal OT on 40 male subjects in a cross-over design administering positive, neutral, and negative valence touch on the arm with velocities targeting C-tactile afferents. OT significantly increased touch pleasantness ratings independent of touch valence (estimated Cohens d = 3), with the effect largely driven by negative stimuli. This study provided the first evidence that OT may enhance rewarding effects of touch, regardless of valence. In addition, the same group administered manual or machine foot massage to 46 male participants. Intranasal OT significantly increased pleasantness ratings for manual massage, supporting the importance of OT for enhancing positive responses to social touch.

The proposed ACTRI pilot research project will identify the effect of subcutaneous oxytocin on experimental pain and pleasant CT stroking. This contribution will be significant as it will provide foundational knowledge about the role of peripheral OT in perception of affective touch and pain. This is important because pathological states alter affective touch perception and may involve corresponding changes in the role of peripheral OT in affective touch pathways, with potential significance for therapeutic use of peripheral OT. The central hypothesis is that OT will reduce pain threshold and ratings of pain intensity and unpleasantness for thermal, mechanical, and pressure pain. Further, we predict that OT will increase touch pleasantness of slow versus fast stroking and will increase heart rate variability. This research will advance our understanding of the mechanisms of touch-based therapies, such as massage, and identify potential targets for noninvasive modulation of affect and pain.

## 8. PROGRESS REPORT

None, this is an initial application.

#### 9. RESEARCH DESIGN AND METHODS

All procedures in this study are conducted solely for research purposes.

This proposed study includes one baseline calibration session and two experimental testing sessions. To experimentally manipulate local OT in the skin, we will test the effects of subcutaneous injection of OT on the perception of acute pain and affective touch by comparing double-blind injection of 4mcg/2ml OT and isotonic saline placebo (2ml) on pain perception.

## Pre-Study Screening Procedures

Interested individuals will complete the phone screening. This includes basic demographic and contact information as well as questions targeting medical inclusion and exclusion criteria (see Phone Screen Attachment).

## Consent

Inclusion/exclusion criteria will be confirmed at the start of each session before consent is signed. Consent will be administered in-person in the ACTRI clinic at UCSD, at the beginning of Session 1. A member of the study team will discuss the consent form and answer any questions that may arise.

## Baseline measures:

After consent is signed, basic demographic data will be confirmed from the phone screen record and logged in study records (name, date of birth, age, gender, sex at birth, ethnicity, race, telephone number, email address, current medications, and handedness). Current medications will be reviewed and updated at the beginning of each session. Participants will be asked questions regarding their recent food, alcohol, and caffeine intake, smoking, exercise, and sleep to assess as study covariates.

